14.3 Appendix 3: Eastern Cooperative Oncology Group (ECOG) performance status

Score	Performance status
0	Fully active, able to carry on all pre-disease performance without restriction.
1	Restricted in physically strenuous activity but ambulatory and able to carry out work of a light or sedentary nature, e.g. light housework, office work.
2	Ambulatory and capable of all self-care but unable to carry out any work activities. Up and about more than 50% of waking hours.
3	Capable of only limited self-care, confined to bed or chair more than 50% of waking hours.
4	Completely disabled. Cannot carry on any self-care. Totally confined to bed or chair.
5	Dead

14.4 Appendix 4: Adaptive Basket Trial for Combination Immune-therapy in Patients with Advanced Solid and Lymphoma

1 Introduction

This document outlines the adaptive design framework to be used for a single-arm Phase II study for the investigation combination immune-therapy across multiple cancer subtypes.

Seven pre-specified tumor cohorts, (also referred to as “groups”) are planned for the analysis:

Small-cell lung cancer (SCLC)	Gastroesophageal
Soft tissue sarcoma (STS)	Prostate
Ovarian	Advanced NET
Diffuse large B-cell lymphoma (DLBCL)	

The primary endpoint in each group is clinical benefit rate (CBR) assessed at 24 weeks. All patients will receive the experimental treatment.

The trial incorporates analyses based on a hierarchical model that allows for the possibility that the effect profile for the population of tumor types may be homogeneous or heterogeneous. There may be ‘clusters’ or subsets of tumor types – some in which the treatment is effective, and others not. The analysis borrows information, in a limited sense, from the tumor types that demonstrate similar CBR effects based on the trial data. The clustering used to characterize the distribution of tumor via a Dirichlet process prior (Escobar & West, 1995; Neal, 2000) is solely based on the observed CBRs. As described in Berry et al. [Berry, 2013], borrowing via a hierarchical model is a type of shrinkage estimation; it provides a formal mechanism by which extreme observations are shrunk toward the mean.

Prospectively, the model is developed by evaluating its performance from simulated trials. Hence, the false-positive rate can be controlled and power assessed. The advantages to borrowing are 1) increased precision of CBR estimates and 2) better decisions regarding CBRs.

2 Primary Analysis

We let Y_i be the response indicator for the i^{th} subject. We define $\pi_g = \Pr(Y_i = 1 \mid g_i = g)$ as the underlying probability of clinical benefit for group g for the experimental treatment and R_g as the assumed probability of clinical benefit for group g within the control population. We transform to the logit scale for modeling purposes. Let θ_g be the mean log odds treatment effect, i.e.:

$$\theta_g = \log\left(\frac{\pi_g}{1 - \pi_g}\right) - \log\left(\frac{R_g}{1 - R_g}\right).$$

Thus, θ_g is the logistic regression coefficient for the treatment within group g . The primary analysis is a set of group specific tests of $\theta_g > 0$, meaning that the treatment is better than the assumed control rate within that group. Thus, we wish to test the set of hypotheses

$$H_{0g} : \theta_g \leq 0,$$

$$H_{1g} : \theta_g > 0.$$

We proceed in a Bayesian fashion, assigning a prior distribution (discussed below) and computing the posterior probability of H_{1g} within each group g . If, at the final analysis,

$$\Pr(\theta_g > 0 | \text{data}) > 0.80,$$

then group g will be declared a success. Hence, the final analysis produces a separate decision for each group. The trial allows for early stopping of groups for futility, described below. No early stopping for success is allowed.

3 Trial Logistics

For the primary population for which primary analyses, including the hierarchical modeling, will be conducted, the maximal sample size is 24 subjects per group. An additional 6 subjects per group may be enrolled in an exploratory population but will not be included in the primary analysis.

In simulations, interim analyses are conducted every 13 weeks, with the first interim analysis occurring once any group has 5 subjects with CBR data or 10 subjects are enrolled. In practice, interims will be spaced such that 3 months have elapsed since the previous interim AND at least 10 additional subjects contribute new CBR data to the next interim.

Interim decisions are driven by $\Pr(\theta_g > 0 | \text{data})$, the probability that the treatment is better than control (this is the same probability that drives the final analysis).

At each interim, $\Pr(\theta_g > 0 | \text{data})$ is computed for each group. If at any interim $\Pr(\theta_g > 0 | \text{data})$ is too small (<0.20) the group is stopped for futility. To expand enrollment beyond 10 subjects, $\Pr(\theta_g > 0 | \text{data})$ must be sufficiently large (>0.70) at the most recent interim. Note interims are not conducted at the time of enrolling the 11th subject in a group, but rather the most recent interim results are used for expansion. If $\Pr(\theta_g > 0 | \text{data})$ is not sufficiently large and 10 subjects are already enrolled in a group, the group will pause enrollment (it is not futile, simply not promising enough for more investigation). Should this probability reach the required level at a later interim analysis, enrollment may start again and the group sample size would then expand from 10 to 24 subjects. Once a group expands beyond 10 subjects, if at any future time $\Pr(\theta_g > 0 | \text{data})$ shrinks sufficiently low (<0.60) the group is stopped for futility. Thus, should an expansion be started but the expansion data not be trending in the right direction (toward the needed 0.80 at the final analysis), the expansion will be halted. A minimum of 5 subjects with CBR data will be required in a group before it may discontinue enrollment for futility or expand from 10 to 24 subjects.

Enrollment will continue until no more subjects can be enrolled and all current subjects have completed 24 weeks of follow-up. This occurs when all groups have either stopped for futility, enrolled to 24 subjects, or enrolled to 10 subjects and are not expanding. The final analysis will occur once enrollment is complete and all subjects have been followed to their endpoint.

4 Statistical Modeling

We let Y_i be the response indicator for the i^{th} subject. We define $\pi_g = \Pr(Y_i = 1 | g_i = g)$ as the underlying probability of clinical benefit for group g for the experimental treatment and R_g as

the assumed probability of clinical benefit for group g within the control population. We transform to the logit scale for modeling purposes. Let θ_g be the mean log odds treatment effect, i.e.:

$$\theta_g = \log\left(\frac{\pi_g}{1 - \pi_g}\right) - \log\left(\frac{R_g}{1 - R_g}\right).$$

The statistical design borrows information across subgroups with a hierarchical model. The hierarchical model allows dynamic borrowing of information between groups such that more borrowing occurs when the groups are consistent and less borrowing occurs when the groups differ. In this way, the model is a compromise between the extremes of a completely pooled analysis as opposed to a separate analysis in each group. We additionally incorporate a clustering mechanism that allows borrowing within clusters but treats clusters separately. This minimizes borrowing across groups that are quite different in terms of CBR effects.

The purpose of such an analysis (discussed in more detail in the appendix) is to produce higher power or lower type I error in situations where we see some commonality (identical effects are not required) among the groups. The model will borrow more in situations where the groups appear similar than in situations where the groups appear different.

4.1 Hierarchical Model with Clustering

Our hierarchical approach involves two stages. The goal of both stages is to allow the data to drive the amount of borrowing across groups. If the data indicate a large amount of borrowing is appropriate (due to similar results), the model will borrow more and thus increase the overall power of the trial within each group. In contrast, if the data indicate a small amount of borrowing is appropriate (due to dissimilar results) the model will adjust and each group will stand more on its own. This “dynamic” borrowing property is distinct from other approaches which use a fixed informative prior or *apriori* assume an amount of borrowing across groups. Here the approach includes two stages to identify the appropriate amount of borrowing based on the data.

The first stage of model places the groups into distinct clusters. The purpose of this stage is to minimize borrowing of information across groups that appear to be quite different. Thus, for example, should 2 of the groups appear similar while the others differ significantly, the model may place a large probability on two clusters, one containing the two similar groups with the other containing the remaining groups. The model does not pick one particular clustering, but instead incorporates the uncertainty of the data in this determination, producing a probability distribution over the possible clusterings. Thus, in our example, the model may consider it highly likely that the 2 similar groups are in one cluster with the remaining groups in another, but it would also retain lower probabilities on the possibility all groups are in one cluster (e.g. we are simply seeing differences in the two groups by chance) as well as other possibilities. The complete analysis averages over this uncertainty. This clustering approach is implemented through a Dirichlet Process Mixture (DPM) model, described in the appendix.

At the second stage, we place hierarchical models over the groups within each cluster (thus, conditional on the clustering, there is no borrowing of information across clusters, only within clusters). The hierarchical model assumes that the θ_g have an across groups distribution

$$\theta_g \sim N(\mu, \tau^2)$$

The across groups mean μ and variance τ^2 are unknown, and hence have a prior distribution which is combined with the data to produce estimates of μ and τ^2 .

The variance component τ controls the degree of borrowing among groups. Small values of τ result in a greater degree of borrowing while large values of τ correspond to less borrowing. The parameter τ is estimated using the data, so the observed between group variation is a key component of the model behavior.

Combined, the two stages allow groups with similar results to borrow information between them (they will have a high probability of being in the same cluster) while groups with different results will borrow far less information between them (they will have a low probability of being in the same cluster).

Details of the two stages may be found in the Appendix.

5 Evaluation of Trial Futility, Sample Size Expansion, and Success

Interim monitoring will occur once 5 subjects have CBR data available within a group or 10 subjects have been enrolled within a group. Interim analyses will continue every 3 months thereafter provided at least 10 subjects contribute new CBR data to the subsequent interim. Simulation studies in this document approximate this interim plan, as they are timed 13 weeks apart without any restrictions on the number of new observations within the analysis.

At each interim analysis, the groups will be evaluated for early futility and sample size expansion by comparing posterior quantities for the CBR to pre-specified early stopping criteria.

5.1 Early Futility

If there is less than 20% probability that the clinical benefit rate in a group exceeds the historical rate R_g , then the group will stop enrollment early for futility. Formally, enrollment will stop early for futility if:

$$\Pr(\pi_g > R_g) < 0.20.$$

A group is only eligible for early stopping once a minimum of 5 subjects has been evaluated for response in that group.

5.2 Sample Size Expansion

If there is at least 70% probability that the clinical benefit rate in a group exceeds the historical rate, then the group is eligible to expand its overall sample size from 10 to 24 subjects. Formally, a group is eligible to expand if, at the last conducted interim:

$$\Pr(\pi_g > R_g) > 0.70.$$

A group is only eligible for sample size expansion once a minimum of 5 subjects has been evaluated for CBR in that group. This eligibility remains effective until the next interim analysis is conducted, at which point eligibility is re-evaluated based on the currently available data and corresponding model outcomes.

5.3 Post-Expansion Futility

If there is less than a 60% probability that the clinical benefit rate in a group exceeds the historical rate, then the group will stop enrollment early for futility. Formally, enrollment will stop early for futility if:

$$\Pr(\pi_g > R_g) < 0.60.$$

A group is only eligible for this post-expansion stopping criterion once the group has expanded to a sample size beyond 10 subjects enrolled. Note this post-expansion futility is a stricter futility rule than that used prior to sample size expansion.

5.4 Final Analysis

The final analysis will occur when both accrual and follow-up are complete in all groups. If, at the completion of the trial, there is at least 80% probability that the clinical benefit rate in a group exceeds the historical rate, then the group will be considered a success. Formally:

$$\Pr(\pi_g > R_g) > 0.80.$$

6 Simulation

Extensive simulations have been conducted to develop and understand the performance of the adaptive design, the hierarchical model including clustering mechanism, interim monitoring, and decision criteria. We evaluated the design under a variety of possible “truths” for the underlying CBR within each group.

6.1 Simulation Assumptions

6.1.1 Trial Enrollment

The assumed average accrual is 124 subjects in 18 months across the 7 groups. The average group rate of accrual varies by group, with some groups enrolling at a faster rate than others. Hypothetical yearly accrual rates are provided in Table 1. It is anticipated that the yearly accrual rates will vary by group, but based on a different pattern across groups than that assumed for simulations. A Poisson distribution with these assumed mean rates dictate trial entry for simulated subjects. Hence, actual accrual rates within each simulated trial will vary from the mean based on this distributional assumption.

No dropouts are assumed for this simulation; hence, the final endpoint will be observed for every subject.

6.1.2 Historical Control Rates

The assumed control CBRs (R_g) vary by group and are provided in the below table. Many of these rates are not directly available in the literature. Rather, we have estimated the CBR based on estimates of the median PFS time (and assuming exponential PFS). The median PFS times and estimated historical CBR rates are shown in Table 1. Because these rates vary, a numbering scheme (1 through 7) is used in simulations and corresponding results to index the 7 groups.

Group Index	Tumor Type	Median PFS (mo)	Hist. CBR (%)	Hypothetical Yearly Average Accrual (Subjects)
1	SCLC	1.5	6.25	20
2	Gastroesophageal	5	43.50	16
3	STS	6.2	51.10	13
4	Prostate	4	35.40	11
5	Ovarian	3	25.00	10
6	Advanced NET	5	43.50	7
7	DLBCL	3	25.00	6

Table 1 – Historical CBR for each group

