7.1 Study flow and visit schedule

[Table 7-1](#) lists all of the assessments and indicates with an “X”, the visits when they are performed. All data obtained from these assessments must be supported in the patient’s source documentation.

No CRF will be used as a source document.

Screening/baseline evaluations must be performed \leq 21 days before Cycle 1 Day 1. Assessments required on Cycle 1 Day 1 that are performed as part of the screening evaluations and within 4 days prior to the first dose of study treatment, do not need to be repeated on Cycle 1 Day 1 (except Pregnancy test which needs to be completed within 72 hours prior to the first dose). Laboratory and radiological assessments performed as part of standard of care prior to signing informed consent may be used if performed within the screening time window.

During the course of the study visits, test and/or procedures should occur on schedule whenever possible. A visit window of +/- 4 days is allowed for visits and a window of +/- 7 days is allowed for radiological assessments.

For the 30-day and 150-day safety follow-up visits, a window of +7 days is allowed. For the 60-day, 90-day, and 120-day safety follow-up, a window of \pm 14 days is allowed.

If the infusion of either study drug is delayed (see [Section 6](#)), the visit will be shifted accordingly.

Table 7-1 Visit evaluation schedule (Cycle Length is 21 days/ 3 weeks)

	Protocol Section	Screening					Cycle 3	Subsequent Cycles	End of study treatment (EoT)	Safety Follow up
			Cycle 1		Cycle 2					
Visit Name		1	2	3	4	5	6	7,8,9...		
Day of cycle			1	8	1	8	1	1		30, 90, & 150 60 & 120
Adverse events	8.1	Continuous								
Prior/concomitant medications	6.4	Continuous								
Surgical and medical procedures		Continuous								
Study Drug administration LAG525(Q3W)	6.1		x		x		x	x		
Study Drug Administration PDR001(Q3W)	6.1		x		x		x	x		
Imaging and radiological tumor assessment	7.2.1	x			Every 6 weeks starting at week 12 through week 24 and every 12 weeks thereafter					
Serum prostate-specific antigen (PSA) (Prostate cancer only)	7.2.1.1.1	x			Every 6 weeks starting at week 12 through week 24 and every 12 weeks thereafter					
Cancer Antigen-125 (ovarian cancer only)	7.2.1.1.2	x			Every 6 weeks starting at week 12 through week 24 and every 12 weeks thereafter					
Measurement of superficial disease (if present)	7.2.1.1.3	x			Every 6 weeks starting at week 12 through week 24 and every 12 weeks thereafter					

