7.2.1.1 Radiological Tumor Assessment

At screening, all patients will undergo CT with i.v. contrast of the chest, abdomen and pelvis. Additionally, patients with lymphoma will also undergo CT with i.v. contrast of the neck and a PET scan. MRI should only be used to evaluate sites of disease that are not adequately imaged by CT. If a patient is intolerant of iodine-based contrast agents, CTs may be performed without contrast. MRI may be used to evaluate sites of disease where a CT without i.v. contrast is not adequate. Visible skin lesions and easily palpable subcutaneous tumors may be measured by physical examination using a ruler or calipers. Ultrasound should not be used to measure sites of disease.

No modality change would be allowed during the study when assessing overall tumor status. For subsequent scans in the same patient, the radiologist must account for all lesions that were present at screening and must use the same technique as used at screening. If possible, a single radiologist should perform all tumor response evaluations for an individual patient. Only in exceptional cases when during the study a patient develops intolerance to the CT scan contrast medium, a CT scan without contrast will be acceptable to avoid modality change.

Tumor assessments will be performed at the time points specified in [Table 7-1](#).

Radiological disease assessments will be performed every 6 weeks (± 7 days), starting 12 weeks after first dose of study drug and continuing through week 24. The frequency of radiological disease assessments will be reduced to every 12 weeks after patients have completed 24 weeks on treatment and will continue until confirmed disease progression. Solid tumor response will be determined locally according to RECIST 1.1 (Appendix 1). Lymphoma response will be determined locally according to Revised Response Criteria for Malignant Lymphoma, (Cheson et al 2007) (Appendix 2).

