10.4.3 Evaluation of trial success and futility

Interim monitoring will occur once 5 subjects have CBR data available within a cohort. Interim analyses will continue every 3 months thereafter provided at least 10 subjects contribute new CBR data to the subsequent interim. Simulation studies in this document approximate this interim plan, as they are timed 12 weeks apart without any restrictions on the number of new observations within the analysis.

At each interim analysis, the groups will be evaluated for early futility and sample size expansion by comparing posterior quantities for the CBR to pre-specified early stopping criteria.

Table 10-1 Historical CBR for each group

Group Index	Tumor Type	Median PFS (mo.)	Hist. CBR (%)	Hypothetical Yearly Average Accrual (Subjects)
1	SCLC	1.5	6.25	20
2	Gastroesophageal	5	43.50	16
3	STS	6.2	51.10	13
4	Prostate	4	35.40	11
5	Ovarian	3	25.00	10

6	Advanced NET	5	43.50	7
7	DLBCL	3	25.00	6

Early Futility

If there is less than 20% probability that the response rate in a subgroup exceeds the historical rate R_g , then the group will stop enrollment early for futility. Formally, enrollment will stop early for futility if:

$$\Pr(\pi_g > R_g) < 0.20.$$

A group is only eligible for early stopping once a minimum of 5 patients have been evaluated for response in that group.

Early Success

If there is at least 70% probability that the response rate in a subgroup exceeds the historical rate, then the subgroup will stop enrollment early for success. Formally, enrollment will stop early for success if:

$$\Pr(\pi_g > R_g) > 0.70.$$

A minimum of 5 subjects will need to be evaluated prior to declaring a group to be efficacious. This eligibility remains effective until the next interim analysis is conducted, at which point eligibility is re-evaluated based on the currently available data and corresponding model outcomes.

Post-Expansion Futility

If there is less than a 60% probability that the clinical benefit rate in a group exceeds the historical rate, then the group will stop enrollment early for futility. Formally, enrollment will stop early for futility if:

$$\Pr(\pi_g > R_g) < 0.60.$$

A group is only eligible for this post-expansion stopping criterion once the group has expanded to a sample size beyond 10 subjects enrolled. Note this post-expansion futility is a stricter futility rule than that used prior to sample size expansion.

Final Analysis

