6.3 Results

6.3.1 Probability of Group Success

We evaluated the probability of group success for each group in each of the six scenarios for the distribution of assumed true CBRs for each group. If the group is truly effective (great or moderate), this represents the power for detecting this effect in the group. For groups where the treatment is truly ineffective (null), declaring trial success represents a mistake. Our goal is to correctly classify the 7 groups into effective and ineffective groups.

Table 3 shows the probability of success by group. Entries in red represent groups where the treatment effect is 0 (e.g. the treatment is ineffective). Entries in green appear where the treatment is great, and thus indicate the power of the design. Entries appear in blue for a moderate effect, also indicating the power of the design. Results are provided in tabular and graphical format.

Group	Hist. CBR (%)	All Great	All Null	Half	2 Great	2 Null	Mixed
1	6.25	0.565	0.049	0.399	0.095	0.445	0.232
2	43.50	0.809	0.126	0.231	0.638	0.266	0.694
3	51.10	0.824	0.108	0.715	0.161	0.750	0.199
4	35.40	0.802	0.118	0.199	0.156	0.718	0.430
5	25.00	0.769	0.082	0.663	0.584	0.220	0.635
6	43.50	0.810	0.099	0.186	0.140	0.738	0.187
7	25.00	0.762	0.088	0.636	0.138	0.667	0.395

Table 3 – Probability of group success

The probability of trial success is dependent upon the historical control rates and distribution of true CBRs across the groups. When the treatment effects are the same across all groups (All Great, All Null), estimation efficiencies, due to borrowing, result in strong trial performance. In the All Null scenario the individual groups have less than a 13% chance of mistakenly declaring group success. In the All Great scenario, power generally ranges from 76.2%-82.4%. The groups that have a small historical control rate tend to have lower power. This is due to the selection of scenarios whereby power is assessed for detecting a 0.7 log-odds improvement, which is more difficult for lower historical control rates. In addition, the global type I error (proportion of trials that declare at least one group successful in the All Null scenario) is controlled at 0.431.

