Interim monitoring will occur once 5 subjects have CBR data available within a cohort. Interim analyses will continue every 3 months thereafter provided at least 10 subjects contribute new CBR data to the subsequent interim. Simulation studies in this document approximate this interim plan, as they are timed 12 weeks apart without any restrictions on the number of new observations within the analysis.

At each interim analysis, the groups will be evaluated for early futility and sample size expansion by comparing posterior quantities for the CBR to pre-specified early stopping criteria.

Table 2-1 Historical CBR for each group

Group Index	Tumor Type	Median PFS (mo.)	Hist. CBR (%)	Hypothetical Yearly Average Accrual (Subjects)
1	SCLC	1.5	6.25	20
2	Gastroesophageal	5	43.50	16
3	STS	6.2	51.10	13
4	Prostate	4	35.40	11
5	Ovarian	3	25.00	10
6	Advanced NET	5	43.50	7
7	DLBCL	3	25.00	6

Early Futility

If there is less than 20% probability that the response rate in a subgroup exceeds the historical rate R_g , then the group will stop enrollment early for futility. Formally, enrollment will stop early for futility if:

$$\Pr(\pi_g > R_g) < 0.20.$$

A group is only eligible for early stopping once a minimum of 5 patients have been evaluated for response in that group.

Early Success

If there is at least 70% probability that the response rate in a subgroup exceeds the historical rate, then the subgroup will stop enrollment early for success. Formally, enrollment will stop early for success if:

$$\Pr(\pi_g > R_g) > 0.70.$$

A minimum of 5 subjects will need to be evaluated prior to declaring a group to be efficacious. This eligibility remains effective until the next interim analysis is conducted, at which point eligibility is re-evaluated based on the currently available data and corresponding model outcomes.

Post-Expansion Futility

If there is less than a 60% probability that the clinical benefit rate in a group exceeds the historical rate, then the group will stop enrollment early for futility. Formally, enrollment will stop early for futility if:

$$\Pr(\pi_g > R_g) < 0.60.$$

A group is only eligible for this post-expansion stopping criterion once the group has expanded to a sample size beyond 10 subjects enrolled. Note this post-expansion futility is a stricter futility rule than that used prior to sample size expansion.

Final Analysis

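### The historical CBR bars are 6.0-month rates but the endpoint is at 24 weeks (5.52 months), so under the protocol's own model every bar is 1.5 to 3.0 points too low

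*Protocol*

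**What the plan says.** Appendix 4, Section 1 sets the endpoint: "The primary endpoint in each group is clinical benefit rate (CBR) assessed at 24 weeks". Protocol 10.4.1 and SAP 2.5.1 also put it at week 24.

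Appendix 4, Section 6.1.2 explains that many of the control rates were not directly available in the literature, and continues: "we have estimated the CBR based on estimates of the median PFS time (and assuming exponential PFS". Its Table 1 lists the medians and the resulting rates, and no evaluation time is given. The same rates are repeated in Protocol 10.4.3 ("Table 10-1 Historical CBR for each group") and SAP 2.5.2 ("Table 2-1 Historical CBR for each group").

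Scans are scheduled at weeks 12, 18 and 24. Protocol 7.1 says "a window of +/- 7 days is allowed for radiological assessments". After that, under Protocol 7.2.1.1, "The frequency of radiological disease assessments will be reduced to every 12 weeks after patients have completed 24 weeks on treatment".

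On missing data, Appendix 4, Section 6.1.1 says: "No dropouts are assumed for this simulation; hence, the final endpoint will be observed for every subject".

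**The concern.** R_g is the reference for θ_g and the threshold in each decision rule: futility below 0.20, expansion above 0.70, post-expansion futility below 0.60 and final success above 0.80. It is also the null truth in the simulations. PFS falls with time, so a rate read at a later time than the endpoint is too low a hurdle. All seven bars are displaced in the same direction, so borrowing across cohorts cannot average the displacement out.

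A drug with no effect at week 24 would therefore expand and pass more often than Appendix 4, Table 3 suggests. Table 3 and the global 0.431 are correct when the truth equals R_g. They do not describe a no-effect drug at week 24 under the same model.

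**Working it through.** **Inputs.** Medians and bars are from Appendix 4, Table 1. The endpoint is at 24 weeks = 168 days. The month is 30.4375 days (365.25/12), or 30.3475 days in SAP 2.1.1.9. The scan window is ±7 days.

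**Formula.** Exponential PFS gives R_g = 0.5^(t/median).

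**Reproducing the plan.** With t = 6.0 months every tabulated rate is matched within 0.05 points. Solving each rate for t gives 5.99 to 6.01 months in all seven groups.

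**At the endpoint.** t = 168/30.4375 = 5.52 months, or 168/30.3475 = 5.54 with the SAP month. The latest in-window week-24 scan is day 175, t = 175/30.4375 = 5.75 months. Six months is day 6.0 × 30.4375 = 182.6, when no scan is scheduled.

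| Cohort | Median (mo) | Plan R_g (%) | t = 6.0 | t = 5.52 (24 wk) | Gap | t = 5.54 (SAP month) | t = 5.75 (25 wk) |
|---|---|---|---|---|---|---|---|
| SCLC | 1.5 | 6.25 | 6.25 | 7.80 | 1.55 | 7.75 | 7.02 |
| Gastroesophageal | 5 | 43.50 | 43.53 | 46.53 | 3.03 | 46.42 | 45.07 |
| STS | 6.2 | 51.10 | 51.13 | 53.95 | 2.85 | 53.85 | 52.58 |
| Prostate | 4 | 35.40 | 35.36 | 38.43 | 3.03 | 38.32 | 36.92 |
| Ovarian | 3 | 25.00 | 25.00 | 27.94 | 2.94 | 27.83 | 26.49 |
| NET | 5 | 43.50 | 43.53 | 46.53 | 3.03 | 46.42 | 45.07 |
| DLBCL | 3 | 25.00 | 25.00 | 27.94 | 2.94 | 27.83 | 26.49 |

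The gap is 1.50 to 2.92 points with the SAP month, and still 0.8 to 1.6 points at week 25. On the log-odds scale the 24-week shift is 0.11 to 0.15 in six cohorts and 0.24 in SCLC. That is 16 to 34% of the 0.7 defined as a great effect in Appendix 4, Section 6.2.3.

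**Exact binomial illustration.** This uses the comparator rule of Appendix 4, Section 8 (level 0.20) at n = 24, without interims or borrowing.

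| Cohort | Cut-off at plan R_g | False-positive rate, truth = R_g | Same cut-off, truth = 24-week rate | Cut-off at 24-week R_g |
|---|---|---|---|---|
| SCLC | 3 | 0.187 | 0.287 | 4 |
| Gastroesophageal, NET | 13 | 0.198 | 0.292 | 14 |
| STS | 15 | 0.181 | 0.264 | 16 |
| Prostate | 11 | 0.195 | 0.292 | 12 |
| Ovarian, DLBCL | 9 | 0.121 | 0.204 | 10 |

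**Re-simulation of the adaptive design.** There were 6,000 trials per scenario. The posterior was obtained by numerical integration over μ, τ and all cluster partitions, with α = 2, τ² ~ IG(3, 0.5) and prior variance 1.82 for μ. The Monte Carlo standard error on the any-success rate is about 0.6 points.

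- Calibration at truth = R_g: any success 0.418 (plan 0.431), mean trial size 94.2 (plan 94.3), mean expansions 2.17 (plan 2.187), 'All Great' power 0.546 to 0.807 (plan 0.565 to 0.824).
- Truth at the 24-week rates, bars unchanged: success by cohort, in table order, 0.113, 0.191, 0.202, 0.178, 0.171, 0.186 and 0.170. Table 3, 'All Null', gives 0.049, 0.126, 0.108, 0.118, 0.082, 0.099 and 0.088.
- Any success is then 0.629, and the mean number of successes per trial is 1.21 (0.63 when truth = R_g; plan Table 5 gives 0.7). Reading the μ prior as variance 1.8² also gives 0.63.
- Truth at the 25-week rates: any success 0.516.

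A separate run of 1,000 trials per scenario gave 0.425 at truth = R_g, 0.62 at the 24-week rates and 0.52 at the 25-week rates.

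**The case against.** **The null is defined by R_g.** The hypothesis is θ_g ≤ 0 relative to R_g, so a true rate equal to the 24-week value satisfies the alternative as written. The 0.431 is not miscalculated. This stands, and the 63% should be read as conditional: it is the chance of a success when the drug does nothing at week 24 under the protocol's own model.

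**CBR is not PFS at 24 weeks.** SAP 2.5.3 counts patients without a valid assessment, and unconfirmed responses, as non-responders. Break-even non-evaluable fractions, 1 − (plan R_g)/(24-week rate), are 5.3% for STS, 6.5% for gastroesophageal and NET, 7.9% for prostate, 10.5% for ovarian and DLBCL, and about 20% for SCLC. At those fractions the present bars would be right. In the other direction, SAP 2.5.2 takes best response within the first 24 weeks, which raises CBR. The documents give no rates for either effect, so the net direction for the analysed endpoint is not settled. But Section 6.1.2 itself derives CBR from PFS, no passage presents the lower bar as a missing-data allowance, and neither effect explains a match at 6.0 months in all seven groups.

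**The medians are rough.** Moving from 6.0 to 5.52 months is like multiplying each median by 1.087, which is within whole-month rounding in five of seven cohorts. This is true, but error in the medians can go either way, whereas the time-point offset is fixed, one-directional and removable.

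**A 28-day month.** Protocol 10.4.3 and SAP 2.5.2 treat three-monthly interims as 12 weeks apart, which implies such a convention. Appendix 4, Section 5 says 13 weeks, SAP 2.1.1.9 gives a different month length, and medians quoted in months are not stated to be in 28-day units.

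**Conclusion.** The concern holds. All seven bars are 6.0-month rates set against a 24-week endpoint. Under the protocol's medians and exponential PFS they are low by 1.55 to 3.03 points (1.50 to 2.92 with the SAP month). The scan window does not close the gap.

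With the bars as they stand and true rates at the 24-week values, per-cohort success without effect is 0.11 to 0.20, against 0.049 to 0.126 in Table 3. At least one such success occurs in about 63% of trials (52% if the truth is taken at week 25), against the stated 43.1%.

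These figures rest on the protocol's medians, on exponential PFS, and on CBR equalling PFS at the assessment time. The finding concerns the time point only and does not make the medians more certain.

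**What to change.** Recompute R_g at 24 weeks (7.8, 46.5, 54.0, 38.4, 27.9, 46.5, 27.9%, in table order) in Appendix 4 Table 1, Protocol Table 10-1 and SAP Table 2-1, and state the evaluation time and month length. Update Appendix 4 Table 2, where +0.7 log-odds becomes 14.6, 63.7, 70.2, 55.7, 43.8, 63.7 and 43.8%. Rerun the simulations and restate power and error.

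The work is a table correction and a rerun of existing code. The bar becomes slightly harder: one more responder of 24 per cohort under the exact 0.20 rule (for ovarian and DLBCL this is borderline, since 9 of 24 has tail 0.204). In re-simulation the 24-week bars return the any-false-success rate to 0.43 and keep power at 0.58 to 0.80 for a +0.7 log-odds effect. At the absolute 'All Great' rates now in Table 2, power falls by about 11 to 14 points (0.55–0.81 to 0.41–0.69).

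Timing matters. Seventy patients were enrolled by Amendment 1, and the SAP addendum has entries dated after database lock, so moving the decision bar now would be post hoc. If the bars are kept for that reason, state that they are 6-month rates, and report each cohort's Pr(π_g > R_g) and the error rates against the 24-week R_g beside the planned results.
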